4.2 Scientific Rationale for Study Design

The study design proposed will achieve robust and unbiased results because a randomized controlled experiment is a gold standard approach. To mimic existing double-dollar incentive programs, participants randomized to receive discounts will receive half-off qualifying fruits and vegetables.

4.3 End of Study Definition

The end of study is when we have collected data from 2,692 participants who have completed our online survey on Qualtrics and completed our online grocery shopping task on the “Gorilla” web-based supermarket platform.

5 - Study Population

5.1 Inclusion Criteria

The inclusion criteria include: 1) aged 18-99 years; 2) ability to read and speak English; 3) have ever received SNAP benefits, 4) live with fewer than 5 people; and 5) access to a personal computer, laptop, tablet, or mobile phone.

5.2 Exclusion Criteria

The exclusion criteria include: 1) aged <18 years or >99 years; 2) lack the ability to read and speak English; 3) have never received SNAP benefits, 4) live with 5 or more people; and/or 5) do not have access to a personal computer, laptop, tablet, or mobile phone.

5.3 Lifestyle Considerations

There will be no restrictions during any parts of the study pertaining to lifestyle and/or diet.

5.4 Screen Failures

Screen failures include those who do not meet all of our inclusion criteria. Potential participants will answer four pre-screening questions to determine their eligibility. The pre-screening questions include those related to 1) age; 2) the ability to read and speak English; 3) receipt of SNAP benefits (ever), and 4) the number of household members (we do not explicitly ask about access to a personal computer, laptop, tablet, or mobile phone, since they are using Qualtrics to access our survey, which requires access to such devices). If they do not meet our inclusion criteria, these subjects will see the text "Thank you for your time, but unfortunately, you are not eligible for this study."

Re-screening is not applicable.

5.5 Strategies for Recruitment and Retention

We propose to recruit our sample through CloudResearch, an online research company that recruits volunteer research participants from dozens of online providers. This means that people navigated to the panel website, created an account, and verified their desire to participate in studies by confirming their email address. CloudResearch uses an assignment process to match participants with surveys they are likely to be eligible for and complete, with proprietary quality control procedures to ensure participants do not take the same survey twice. To reduce selection bias associated with the topic of the survey, invitations do not include specific details of the survey. Participants who complete CloudResearch's online surveys receive points that can be redeemed for various incentives, including cash, lotteries, or donations to charity. We have approval from NYU Medical Center Information Technology

(MCIT) to use CloudResearch for recruitment. The online survey is already developed (and uploaded to Research Navigator).

To incentivize participation and truthful responses, we will also notify participants prior to the experiment that they are automatically entered into a lottery to have the items in their shopping cart delivered to their household if they complete both the survey and the shopping trip task.

6 - Study Procedures

The people participating in the study will complete an online survey about what factors motivate or prevent them from shopping for groceries online. After completing the survey, all participants will participate in an online randomized controlled experiment. At the end of the survey, participants will be directed to click the link to our web-based supermarket.

Participants will be asked to select a typical week's worth of food for their household and assume they need to buy the most important things, including the fruits and vegetables they typically buy. Participants will be randomized to one of four conditions. To mimic existing double-dollar incentive programs, participants randomized to receive discounts will receive half-off qualifying fruits and vegetables. The discount will be applied directly to participants' online shopping cart items at point of selection. Participants randomized to healthy bundle defaults with no discount will be offered a bundle of food and beverage items pre-loaded in their online shopping cart (i.e., a healthy default). This bundle will be determined by participants' answers to two questions in the online survey asking which fruits and beverages they purchase most often. Participants randomized to healthy bundle defaults plus a discount will receive a half-off discount on an identical tailored bundle. Participants will be allowed to remove the bundle from their shopping cart. Prior to shopping, participants will be given instructions regarding the discount and/or bundles.

We will recruit a nationwide non probability panel of 2,692 low-income adults >18 years through CloudResearch, an online surveying company that recruits volunteer research participants through their online panels and other online communities. Participants who complete CloudResearch's online surveys receive points that can be redeemed for various incentives, including cash, lotteries, or donations to charity. Potential participants will click the link for our online study and complete an online consent. After providing consent, potential participants will complete four pre-screening questions to determine their eligibility. The pre-screening questions include those related to 1) age; 2) the ability to read and speak English; 3) receipt of SNAP benefits (ever), and 4) the number of household members (we do not explicitly ask about access to a personal computer, laptop, tablet, or mobile phone, since they are using Qualtrics to access our survey, which requires access to such devices). All questions in the survey, including the pre-screening questions, will be completed on a personal computer, laptop, tablet, or mobile phone and will take approximately 10-15

minutes to complete. We will use Qualtrics to create and distribute the survey. At the end of the survey, participants will be asked to simulate one grocery shopping trip in a web-based supermarket and to select a typical week's worth of food for their household, including fruits and vegetables, which will take an additional 10-15 minutes.

We will assess hypothetical purchases, so no payment will be taken and participants will be informed that they will not normally receive the shopping cart items. To incentivize participation and truthful responses, however, participants will be notified prior to the experiment that they are automatically entered into a lottery to have the items in their shopping cart delivered to their household if they complete both the survey and the shopping trip task. Our budget allows us to offer delivery of shopping cart items to one in ten participants. At the end of the study, CloudResearch will reveal to participants who win the lottery that they will be provided with a gift card with the equivalent amount of money loaded onto it that they spent in the study (rather than having the groceries delivered). This approach will mitigate potential issues related to delivery and avoid complications associated with changing grocery stock items. We also anticipate that participants would prefer money they can spend on anything, rather than being restricted to grocery items. CloudResearch will also debrief participants about the purpose of the study, including the justification for providing lottery winners a gift card instead of groceries. The participants who do not win the lottery will also be debriefed.

After completing the online survey, we will randomize all participants from Aim 2 to one of four conditions, including 1) no intervention, 2) discount on eligible fruits and vegetables, 3) healthy bundle defaults with no discount, and 4) healthy bundle defaults plus a discount. All participants will answer the same set of questions in the online survey on Qualtrics. After clicking the link to access the web-based supermarket platform on the "Gorilla" platform, participants will be randomized to one of the four experimental conditions outlined in Aim 3. The "Gorilla" platform has a randomization function built into its design. No blinding will be done.

Adherence to the protocol will be assessed by completion of the online survey data and the "checking out" of our online grocery store with a minimum of two items in the cart (no payment will be taken).

7 - Study Intervention Discontinuation and Participant Discontinuation/Withdrawal

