4.1 Overall Design

This research study includes three aims (see figure below), though only Aim 2 and Aim 3 involve human subjects. The duration of the study is 5 years.

In Aim 1, we will develop the components of healthy bundle defaults (i.e., preloaded cart items) using publically available data from the National Household Food Acquisition and Purchase Survey (FoodAPS), the literature, and expert advice. Specifically, we will measure the frequency of food and beverage purchases in FoodAPS, to enable us to determine the most frequent healthy food purchases by category (e.g., fruits, vegetables) among low-income households by household size, gender, and race/ethnicity. These healthy bundle defaults will be used in Aim 3, specifically the arms with healthy bundle defaults. The development of the bundles will occur in Year 1. Aim 1 does not involve human subjects research.

In Aim 2, we will recruit 2,692 low-income adults aged >18 years from a nationwide nonprobability panel via CloudResearch and administer an online survey to characterize participants' online grocery shopping behaviors and attitudes. After completing the online survey, we will randomize all participants from Aim 2 to one of four conditions, including 1) no intervention, 2) discount on eligible fruits and vegetables, 3) healthy bundle defaults with no discount, and 4) healthy bundle defaults plus a discount.

In Aim 3, participants will click a link and simulate a shopping experience by selecting a week's worth of SNAP-eligible groceries for their household in a web-based supermarket platform. We will also use Cauldron Science Ltd., which provides subscribers with access to their web-based tool "Gorilla". "Gorilla" allows researchers to plan, design, and carry out online psychology experiments for research purposes, including a supermarket platform. The platform is already built and we have a license to use it for our experiment, with approval

from the NIH, approval from NYU Medical Center Information Technology (MCIT), and a fully executed contract via the NYU legal office.

We will examine the impact of our behavioral economic strategies on the proportion of real dollars spent on total fruits and vegetables per online shopping basket. We will also explore whether the impact of our intervention on food purchases differs by sociodemographics. Data collection for Aims 2-3 will occur in Years 2-4.

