9.1 Statistical Hypotheses

We will test the working hypothesis that the likelihood of shopping online for groceries is higher among adults who are male, White, and younger; and that adults who shop online will have higher adjusted odds of consuming at least 5 daily servings of fruits and vegetables than those who do not shop online. We also hypothesize that participants exposed to healthy bundle defaults plus a discount will spend more on fruits and vegetables than controls; and that the effect size will be larger relative to arms with only discounts or only bundles.

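### Condition 4's discount is described in two ways; if it covers only the bundle, bundle-plus-discount versus discount-only does not isolate the effect of adding the bundle

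*Combined protocol and SAP*

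**What the plan says.** Section 4.1 and Section 6 list four conditions: 1) no intervention, then "2) discount on eligible fruits and vegetables, 3) healthy bundle defaults with no discount, and 4) healthy bundle defaults plus a discount". Condition 2's label names the items discounted; condition 4's label does not.

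Two sentences then define the discount:

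- **General rule** (Synopsis under Description of Study Intervention and again under Participant Duration, Section 4.2, Section 6): "participants randomized to receive discounts will receive half-off qualifying fruits and vegetables".
- **Rule specific to condition 4** (Synopsis under Description of Study Intervention, Section 6): "Participants randomized to healthy bundle defaults plus a discount will receive a half-off discount on an identical tailored bundle".

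On the bundle itself, condition 3 participants "will be offered a bundle of food and beverage items pre-loaded in their online shopping cart". Its contents depend on "two questions in the online survey asking which fruits and beverages they purchase most often". The bundle is therefore not confined to fruits and vegetables, and it is described as the same in conditions 3 and 4.

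Section 9.1 predicts higher fruit and vegetable spending in condition 4 than in control. Against the two single-component conditions, it predicts that "the effect size will be larger relative to arms with only discounts or only bundles". The Aim 3 endpoint (Section 9.4.2) is the share of basket dollars spent on fruits and vegetables. The model regresses it on condition indicators with control as reference.

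**The concern.** To learn what a default bundle adds to a fruit and vegetable discount, condition 4 has to be condition 2 with the bundle added. Under the sentence specific to condition 4, it is not. Fruits and vegetables outside the bundle are half price in condition 2 and full price in condition 4, while bundle items that are not fruits or vegetables are half price only in condition 4. The comparison then changes two things at once.

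At stake is the discount-only part of the Section 9.1 prediction. A null or reversed result could come from the narrower discount and not from a weak bundle; a favourable result could come partly from how discounted dollars enter the endpoint. The difference lies in what is delivered, and no condition pairs the bundle with condition 2's discount, so no covariate or added contrast can separate the two afterwards.

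The ambiguity matters in itself: two builds of the shopping platform could each follow the protocol and give condition 4 different interventions.

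**Working it through.** **1. Readings of condition 4.** The text permits three.

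| Reading | Discounted in condition 4 | Condition 4 minus condition 2 |
|---|---|---|
| General rule only | Qualifying fruits and vegetables | Bundle added |
| Specific rule only | Bundle items | Bundle added, discount moved to other items |
| Both | Qualifying fruits and vegetables, and all bundle items | Bundle added, plus a discount on its other items |

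**2. The Section 9.1 comparisons under the specific rule.**

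- Condition 4 versus control: unaffected.
- Condition 4 versus condition 3: same bundle, with and without a discount. This is a clean test of discounting the bundle, though not an estimate of condition 2's discount.
- Condition 4 versus condition 2: a valid randomized comparison of two packages, but the difference cannot be assigned to the bundle.

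**3. The plan's sample size (Section 9.2).** 158 × 4 = 632; 632 × 4 = 2,528; 2,692 / 4 = 673 per condition if allocation is equal. The 158 cannot be confirmed, because no standard deviation (SD) or power is given. Reading the 9% as an absolute 0.09, with two-sided alpha 0.05 (stated for Aim 2 only) and 80% power assumed, the implied SD is 0.09 / [(1.960 + 0.842) × √(2/158)] = 0.286. None of these figures changes under this point.

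**4. Counting effect of scope.** Section 9.4.2 does not say whether real dollars means before or after the discount. Assume a basket of $30 fruits and vegetables and $70 other items at list price, the same quantities in both conditions, and dollars counted after the discount. Let c be the bundle's share of fruit and vegetable spending (not given in the documents), with no other bundle items discounted.

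- Condition 2: 15 / (15 + 70) = 0.176.
- Condition 4, bundle-only discount: F = 30 − 0.5 × c × 30; share = F / (F + 70).

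| c | F | Condition 4 share | Minus condition 2 |
|---|---|---|---|
| 0.25 | 26.25 | 0.273 | +0.096 |
| 0.50 | 22.50 | 0.243 | +0.067 |
| 0.75 | 18.75 | 0.211 | +0.035 |

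Behaviour is the same in every row, yet condition 4 looks better. At list price both shares are 30/100 = 0.30 and the shift is zero.

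**5. Behavioural effect of scope.** Now count at list price. Assume the full discount raises the share by D = 9 points (the 9% read as absolute), the bundle raises it by b, effects add, and the discount's effect is proportional to c. Condition 4 minus condition 2 is b + cD − D = b − (1 − c)D. With equal scope it would be b. The narrower discount therefore costs condition 4 (1 − c) × 9 points: 6.75, 4.5 and 2.25 for c = 0.25, 0.50 and 0.75. If b = 5, the observed difference is −1.75, +0.5 and +2.75 points, against +5 with equal scope.

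**6. Scale.** With 673 per condition, the difference detectable at 80% power is (1.960 + 0.842) × SD × √(2/673), which is 0.031, 0.038 and 0.044 for assumed SDs of 0.20, 0.25 and 0.286. The illustrative shifts in steps 4 and 5 run from about 0.02 to 0.10, so many would be large enough to matter. The two sets rest on different assumptions and should not be added.

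**The case against.** The best defence is that the general rule, which appears four times against two for the specific sentence, is worded for everyone randomized to a discount and so naturally includes condition 4. The specific sentence does not say that other fruits and vegetables are full price. This stands: a difference in scope is one reading of inconsistent text, not an established fact. It does not remove the need to reconcile, because the documents never say which rule governs.

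A discounted bundle may also be deliberate. Section 2.2 cites a laboratory-based study of discounted bundles, and the plan neither calls the design factorial nor predicts synergy. This also stands. The sponsor may choose that package, but Section 9.1 then needs to say what its comparison with discount only can show.

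A reader might infer that the combination hypothesis cannot be answered at all. The documents do not support that, as step 2 of the working shows: only one of the three comparisons is affected, and only in its attribution.

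A reader might also infer that the narrower discount biases the result against the combination. That does not follow either. It needs an assumed b, an assumed c and an absolute 9 points, and counting dollars after the discount can push the other way.

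**Conclusion.** The inconsistency is real and can be seen in the text. Its consequence is conditional: under the rule specific to condition 4, the comparison with discount only mixes adding a bundle with changing which items are discounted. A larger, equal or smaller effect than condition 2 could then not be credited to adding the bundle.

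Neither the size nor the direction of the distortion can be fixed from the documents. Both depend on the bundle's share of fruit and vegetable spending and on whether dollars are counted before or after the discount. The illustrations show only that shifts either way could be comparable with the differences the trial can detect; their basket, SDs, bundle effect and additivity are assumptions.

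The point merits action despite its narrow reach, because it decides what one of four conditions receives and cannot be repaired once the data are collected.

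**What to change.** Reconcile the general and specific discount sentences in the Synopsis and in Section 6, so that condition 4's discounted items are stated once and without ambiguity. Then:

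- **If data collection in condition 4 has not begun:** apply the same list of discount-eligible items in conditions 2 and 4, so that condition 4 is condition 2 plus the bundle. Match the participant instructions.
- **If a bundle-only discount is intended or already in use:** label condition 4 a discounted bundle. Keep its comparison with condition 2 as one of two packages, and state in Section 9.1 that it does not isolate the effect of adding the bundle to the fruit and vegetable discount.

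In either case, define in Section 9.4.2 whether dollars are counted before or after the discount.

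The cost of the first option is a price-rule and instruction change in one condition and an IRB amendment; lottery gift-card values there may shift slightly. The second costs a narrower conclusion for one contrast. Neither changes the sample size. The documents do not show whether enrolment has started. If it has, changing the price rule midway would leave condition 4 with two interventions, which is why the first option is limited to the period before its data collection.

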7.1 Discontinuation of Study Intervention

Study modification will occur in the event of an unexpected problem or any necessary change to the protocol. Study team members put in charge of IRB communications will work with the Principal Investigator to prepare, submit, and address comments on modifications.

This study may be discontinued in the event that participants find the gift card instead of delivering grocery items from their shopping cart is too upsetting, although we do not think this is likely since participants would likely prefer money they can spend on anything rather than being restricted to grocery items.

7.2 Participant Discontinuation/Withdrawal from the Study

The participants are allowed to withdraw from the online survey and online grocery shopping experience at any point, with no penalty.

7.3 Lost to Follow-Up

Not applicable.

9 - Statistical Considerations

9.1 Statistical Hypotheses

We will test the working hypothesis that the likelihood of shopping online for groceries is higher among adults who are male, White, and younger; and that adults who shop online will have higher adjusted odds of consuming at least 5 daily servings of fruits and vegetables than those who do not shop online. We also hypothesize that participants exposed to healthy bundle defaults plus a discount will spend more on fruits and vegetables than controls; and that the effect size will be larger relative to arms with only discounts or only bundles.

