9.2 Sample Size Considerations

Based on previous work (40), we require 158 participants in each of the four arms (total n=632) to adequately power our analysis. This sample size provides power to detect a 9% difference between any experimental condition and controls. To allow examination of potential interaction effects by demographic characteristics, we plan a total sample size of 2,692 participants (the rule of thumb that four times the sample size is needed to assess interactions compared to main effects requires us to enroll at least 2,528 participants).

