The primary outcome for Aim 3 is the proportion of real dollars spent on total fruit and vegetables per basket (i.e., shopping cart items) across conditions. We will perform a linear regression to assess balance of demographic characteristics across the four study conditions; because of randomization, these characteristics should be balanced. To assess differences in the proportion of real dollars spent on total fruits and vegetables across experimental conditions, we will regress the outcome variable on indicator variables for the experimental conditions, with the control condition as the reference group; if necessary, we will also adjust for any respondent characteristics that may be unbalanced by condition. The design and methods proposed will achieve robust and unbiased results because a randomized controlled experiment is a gold standard approach.

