9.4.3 Analysis of the Secondary Endpoint(s)

We will test for potential interaction effects by age group, gender, and race/ethnicity. We will also conduct a sensitivity analysis excluding participants who report that they would never consider shopping online for groceries.

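### Section 9.1 hypothesises that bundle plus discount outperforms its components, but the Aim 3 analysis specifies only comparisons with control, with no contrast or decision rule between intervention arms

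*Combined protocol and SAP*

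**What the plan says.** Section 9.1 makes two statements about the experiment. The first is that "participants exposed to healthy bundle defaults plus a discount will spend more on fruits and vegetables than controls". The second, about the same arm, is "that the effect size will be larger relative to arms with only discounts or only bundles".

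The Aim 3 analysis appears in Sections 9.4, 9.4.1 and 9.4.2 in the same form: a linear regression of the outcome on arm indicators, "with the control condition as the reference group", adjusted for unbalanced characteristics if necessary. On the endpoint, Section 9.4.2 says: "The primary outcome for Aim 3 is the proportion of real dollars spent on total fruit and vegetables per basket". Section 9.4.3 adds two analyses: "We will test for potential interaction effects by age group, gender, and race/ethnicity", and "We will also conduct a sensitivity analysis excluding participants who report that they would never consider shopping online for groceries".

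Section 9.2 justifies 158 per arm as follows: "This sample size provides power to detect a 9% difference between any experimental condition and controls". The larger total has a different reason: "To allow examination of potential interaction effects by demographic characteristics, we plan a total sample size of 2,692 participants".

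The two-sided 0.05 threshold is written in the Aim 2 paragraphs. The Aim 3 paragraphs give no alpha.

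**The concern.** Whether combining a default bundle with a discount does better than either alone is a question between intervention arms. The three coefficients of the planned model are each an intervention arm minus control. A larger coefficient for the combination, or significance against control in one arm and not in another, does not test the difference between those arms. Followed as written, the plan never tests the second hypothesis.

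The word joining the two comparators in Section 9.1 is also open: the combination might have to beat both components, or either one. These are different claims with different error rates.

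Two further points bear on what the contrasts would mean. Section 9.1 speaks of spending more, while the endpoint is a share of dollars. And neither Section 3.1 nor Section 9.4.2 says whether dollars are counted before or after the half-price discount.

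**Working it through.** **Hypothesis against analysis.** Write b_D, b_B and b_C for the coefficients of discount only, bundle only and the combination, each against control.

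- First hypothesis in 9.1: b_C > 0. The planned model tests this directly.
- Second hypothesis in 9.1: b_C − b_D > 0 and/or b_C − b_B > 0. Both are linear combinations of planned coefficients, so they are estimable. Sections 9.4 to 9.4.3 name neither.
- Section 9.2: one justification for comparisons with control, one for demographic interactions, none for contrasts between intervention arms.

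**The plan's own figures.** 158 × 4 = 632; 632 × 4 = 2,528; 2,692 / 4 = 673 per arm if allocation is equal. The 158 cannot be reproduced, because the SD, the power and the scale of the 9% are not stated.

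**Results that do not depend on the scale.** With equal arms the two contrasts share the combined arm, so their correlation is 0.5. Z1 and Z2 are the two test statistics (normal approximation, two-sided 0.05, critical value 1.96).

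- Unadjusted separate claims, all three intervention arms equal: 1 − P(Z1 < 1.96, Z2 < 1.96) = 0.045, against 0.025 for one contrast.
- Joint rule (both significant in the combination's favour): the false-claim rate is at most 0.025, reached when one component truly equals the combination and the other is far lower. It is 0.005 when all three are equal. No alpha split is needed.
- A single contrast has 80% power at 1.960 + 0.842 = 2.802 standard errors. With equal gaps, the joint rule has 69% power there and reaches 80% at 3.128 standard errors; 3.128 / 2.802 = 1.117, about 12% larger. At a 90% target the ratio is 1.091.
- With unequal gaps, the smaller gap needed for joint 80% power is about 3% larger than for a single contrast if the other gap is 1.25 times as big (4.49 / 4.36), and under 1% larger at 1.5 times (4.38 / 4.36).

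**Absolute differences, illustration only.** At the same power and alpha, the detectable difference scales with the square root of 1/n, so the SD cancels: 9 × √(158/673) = 4.36.

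| Reading of 9% | Detectable difference, one contrast, 673 per arm |
|---|---|
| Percentage points | 4.36 points |
| Relative, assumed control share 20% (9% × 20 = 1.8 points) | 1.8 × 0.4845 = 0.87 points |
| Relative, assumed control share 30% (9% × 30 = 2.7 points) | 2.7 × 0.4845 = 1.31 points |

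With 80% power behind the 158, the percentage-point row corresponds to an SD of 9 / (2.802 × √(2/158)) = 28.6 points and a contrast SE of 28.6 × √(2/673) = 1.557. The joint rule with equal gaps then needs 3.128 × 1.557 = 4.87 points. The 20–30% control share is an assumption; the documents give none.

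**Dollar counting.** Take an assumed basket of $100 with $30 of fruit and vegetables, all half-price. Counted before the discount, the share is 30/100 = 30%. Counted after it, the share is 15/85 = 17.6%, for identical items. After-discount counting therefore lowers the share in discounted arms mechanically. Combined minus bundle-only is affected because only one of those arms is discounted. Combined minus discount-only is also affected if discount coverage differs.

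**Discount scope.** The Synopsis (Description of Study Intervention) and Section 6 first give everyone randomized to a discount half off qualifying fruits and vegetables, as does Section 4.2. The Synopsis and Section 6 then describe the combined arm's discount as applying to the tailored bundle. The arm lists in Sections 4.1 and 6 mention only a discount.

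**The case against.** The strongest reply is that little is left open. Section 9.1 fixes the combined arm, both comparators and the direction, and Section 9.4.2 fixes the outcome and the model, whose stated purpose is to assess differences across conditions. Given these, the two contrasts are uniquely determined and any statistician can compute them. This stands in large part. A reader might infer that the comparison is left wholly to choice after the data are seen, or that the hypothesis cannot be tested with this design. The documents support neither. But a general purpose followed by a control-referenced model names no test between intervention arms, and it does not settle both versus either, or the alpha.

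A second reply is that the sentence on the combination only hypothesises, whereas the Aim 2 sentence in Section 9.1 promises a test, and the objectives in Section 3.1 do not mention superiority over components. That is fair. A descriptive ranking is therefore an acceptable remedy, provided the plan says so.

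A reader might also infer that the trial is underpowered for these contrasts. The documents do not show that: with no SD, power or scale for the 9%, the detectable difference could be about 4.4 points or about 1.

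On discount scope, the Synopsis and Section 6 do state what the combined arm receives. The more general sentence before it creates the doubt, so this is an ambiguity and not an established contradiction.

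**Conclusion.** The gap is real and should be fixed: a stated Aim 3 hypothesis has no named contrast and no decision rule. It is a gap in specification. No data or estimability are lost, and the missing contrasts leave the comparisons with control unaffected.

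The sizes that do not depend on the scale of the 9% are the 4.5% against 2.5% false-claim rates and the 12% cost of the joint rule at 80% power with equal gaps, falling to almost nothing when one gap is 1.5 times the other. They rest on equal allocation, a common variance and the normal approximation. The absolute detectable differences are conditional illustrations, and the conclusion does not need them.

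Confidence is high for the missing contrasts and rule, and moderate for the discount scope.

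**What to change.** 1. **Contrasts.** In Section 9.4.2, add combined minus discount-only and combined minus bundle-only as linear contrasts from the same regression on the share-of-dollars endpoint, each with a two-sided 0.05 test and a 95% CI. Align the spending wording in Section 9.1 with that endpoint.
2. **Decision rule.** Claim that the combination beats both components only if both contrasts are significant in its favour. If separate claims are wanted, state a multiplicity rule. Otherwise, label the ranking descriptive and report the contrasts with CIs only. The joint rule's downside is the loss of power shown above when the gaps are similar.
3. **Sample size.** In Section 9.2, give the detectable difference for the chosen rule once the SD, the power and the scale of the 9% (absolute or relative) are stated.
4. **Endpoint.** State in Sections 3.1 and 9.4.2 whether dollars are counted before or after the discount.
5. **Discount scope (secondary).** Reconcile the Synopsis with Sections 4.1, 4.2 and 6 on what the combined arm's discount covers; the sponsor decides. If it differs from the discount-only arm, state that combined minus discount-only compares packages and does not isolate bundling.

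The cost is a few sentences, with no additional participants and no new model.
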